#### 8.3 Echocardiographic Endpoints and Parameters

Revision	Date:	August	1,	2022
----------	-------	--------	----	------

For Use Only by Affiliates of Edwards Lifesciences

Title

Statistical Analysis Plan for TRISCEND Study (2019-06)

The TR grade, collected by TTE and assessed by the echo core lab, at screening/baseline, discharge, 30 days, 6 months, 1 year, and annually until 5 years post-procedure will be summarized and plotted using count and percentage of patients who are in each classification category in the AT population. Paired analysis of the following visit compared with the screening/baseline visit will be performed using Wilcoxon signed-rank test if the paired data are more than 15 patients. The number and percentage of patients with moderate or less TR grading at screening/baseline, discharge, 30 days, 6 months, and 1 year will be summarized. The number and percentage of patients with at least one, two, three, four and five TR grade reductions at discharge will be reported. Transthoracic Echocardiogram (TTE) parameters assessed at baseline, discharge, 30 days, 6 months, 12 months, and annually until 5 years post procedure will be summarized using mean, SD, median, minimum, and maximum as well as change from baseline for each variable in the AT population.

Patients that undergo any type of repair or replacement procedure for the tricuspid valve will be excluded from the echocardiographic analysis at the time of the reintervention and summarized in a table.

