#### 3.3 Echocardiographic Endpoints and Parameters

#### 3.3.1 Echocardiographic Endpoint

• The echocardiographic endpoint is reduction in TR grade, measured by comparing the screening/baseline TTE to the discharge TTE. This endpoint will be assessed by the echo core lab using a 5-grade classification system.

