### 6. DATA AND ANALYSIS CONVENTIONS

#### 6.1 General Conventions

For continuous variables, results will be summarized with the number of observations, mean, standard deviation, median, minimum, maximum, and 90% confidence interval (CI) by normal approximation. For categorical variables, results will be summarized with patient count, percentage, and 90% CI by normal approximation, where appropriate.

Survival analysis techniques will be used to analyze time-to-event variables. Patients without events will be censored at their last participation date in the study. For patients who did not have an event but remain in the study, they will be censored at the database extract date. Time to first event curves will be constructed using Kaplan-Meier estimates. Descriptive statistics will be presented at each assessment, including change from baseline to subsequent time point for selected endpoints. For the determination of event rates, the number of patients in the patient population who have had the events or have been followed up to the upper bound of the follow-up visit window will be used as the denominator. Unless otherwise noted, patients with missing data will be excluded from the denominator.

When the sample size is small (e.g., <10 patients), analysis may be performed in the form of listings only.

Quality of life questionnaires will be scored according to algorithms provided by the vendor. The various summary scores produced by the algorithms will be analyzed as continuous variables.

Unless otherwise specified, confidence limits will be two sided, using alpha = 0.05.

Unless otherwise specified, the precise form of each algorithm will be the default of SAS, using the latest release installed at Edwards Lifesciences (Edwards) at the time of analysis.

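### Post-discharge TR-grade percentages labelled As-Treated are conditional on freedom from tricuspid re-intervention, and the SAP should say so and show the re-intervened patients in the denominator

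*SAP*

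**What the plan says.** SAP 8.3 sets the rule: patients who have a tricuspid repair or replacement of any kind "will be excluded from the echocardiographic analysis at the time of the reintervention and summarized in a table". Protocol 12.2 has the same sentence, so the SAP does not depart from the protocol.

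The rule acts on these summaries in SAP 8.3:

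- TR class at every visit to 5 years, as "count and percentage of patients who are in each classification category in the AT population".
- The number and percentage with "moderate or less TR grading at screening/baseline, discharge, 30 days, 6 months, and 1 year will be summarized".
- Wilcoxon signed-rank tests of each follow-up visit against baseline, when more than 15 pairs are available.

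The declared echocardiographic endpoint (SAP 3.3.1) is TR-grade reduction, "measured by comparing the screening/baseline TTE to the discharge TTE". The grade-reduction percentages follow the same timing: patients with "at least one, two, three, four and five TR grade reductions at discharge will be reported".

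On denominators, SAP 6.1 says that, unless otherwise noted, "patients with missing data will be excluded from the denominator". SAP 6.2 restricts analyses to patients with the data the endpoint needs and imputes no echo results. SAP 8.3 has no rule that counts a re-intervened patient as not achieving a TR grade, and it plans no sensitivity analysis on this point.

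**The concern.** Re-intervention happens after treatment and may itself show that the valve has not done its job. Removing such patients from numerator and denominator leaves a percentage among those whose valve has so far needed no second procedure. The As-Treated label does not tell the reader this.

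Some of the excluded data will exist. Under protocol 8.6, a patient with a percutaneous re-intervention that leaves the study device in place stays in follow-up, so later TTEs are due. A patient whose device is explanted leaves after a short safety follow-up and contributes no later echo.

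The SAP handles a similar problem differently elsewhere. In SAP 8.4, a patient who cannot do the walk test for a medical reason is scored as zero distance rather than dropped.

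The study has no control arm, and one of its objectives is to guide later study designs. The TR-grade percentages could therefore be quoted or used for planning without the condition attached to them.

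**Working it through.** **Inputs.** The documents state no re-intervention rate and no expected TR-success rate, so there is no planned figure to reproduce. The sample size of up to 200 (SAP 2.3) has no statistical basis. The values of p, f and q below are assumptions. N = 200 is the enrolment ceiling, used as if every patient had an echo at the visit.

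**Definitions at a given visit.**

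- N: patients who would otherwise be in the denominator
- f: share of N re-intervened by then, so k = fN
- p: share of the remaining N − k with the favourable TR grade, so s = p(N − k)
- q: share of re-intervened patients with a favourable grade on a later echo

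**Formulas.**

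- Planned rule: s / (N − k) = p
- Re-intervention counted as not achieved: s / N = p(1 − f)
- Gap: p − p(1 − f) = p × f
- Later echoes included as observed: p(1 − f) + q × f
- Planned 90% half-width (SAP 6.1, normal approximation): 1.645 × √(p(1 − p)/(N − k))

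**Results for N = 200 and p close to 90%** (whole patients):

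| f (k) | Planned | Counted as not achieved | Gap, points | 90% half-width, points |
|---|---|---|---|---|
| 1% (2) | 178/198 = 89.9% | 178/200 = 89.0% | 0.9 | 3.5 |
| 2.5% (5) | 176/195 = 90.3% | 176/200 = 88.0% | 2.3 | 3.5 |
| 5% (10) | 171/190 = 90.0% | 171/200 = 85.5% | 4.5 | 3.6 |
| 10% (20) | 162/180 = 90.0% | 162/200 = 81.0% | 9.0 | 3.7 |

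**Range over p from 80% to 98%.** The gap is 0.8 to 1.0 points at f = 1%, 4.0 to 4.9 at f = 5% and 8.0 to 9.8 at f = 10%.

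**Gap against sampling error.** The comparison depends on p:

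- p = 80%: 4.0 against 4.8 at f = 5%; 8.0 against 4.9 at f = 10%
- p = 90%: the gap passes the half-width between f = 2.5% and f = 5%
- p = 98%: 1.0 against 1.6 at f = 1%; 2.4 against 1.7 at f = 2.5%

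**Direction under another comparator.** Take p = 90% and f = 5%, and include later echoes as observed. With q = 50% the figure is (171 + 5)/200 = 88.0%. With q = 100% it is (171 + 10)/200 = 90.5%, above the planned 90.0%. The sign is therefore fixed only when re-intervention counts as failure.

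**Which summaries are exposed.** The discharge TTE is done at discharge or day 7, whichever is first (protocol 8.15). Appendix A counts a re-intervention only after the patient leaves the procedure room. The discharge endpoint and grade-reduction percentages can change only through a re-intervention in that interval of at most 7 days. The later TR-class table, the moderate-or-less percentages and the paired tests are exposed throughout.

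**Timing.** The wording suggests that earlier echoes are kept. It does not say whether one visit or all later visits are dropped, so two programmers could produce different tables. The calculation above takes all later visits as dropped.

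**The case against.** The strongest reply is that this is a defensible choice of what to estimate, and that the failures are visible elsewhere. Exclusion avoids crediting the study valve with the result of a second procedure. Re-interventions are reported in several places:

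- the separate table required by SAP 8.3;
- the non-elective MAE component and Kaplan-Meier rates (SAP 8.1 and 8.4);
- clinical success, which a non-elective re-intervention within 30 days defeats;
- exploratory device success (SAP 3.7.2), from 30 days to 5 years, which needs both freedom from unplanned device- or access-related procedures and a TR reduction of at least one grade;
- exploratory individual patient success at 12 months (SAP 3.7.4), which a re-intervention for TR or heart failure defeats.

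Much of this stands, and it lowers the severity. It does not change the TR-grade percentages themselves, and the composites have too many parts to recover them. The MAE and Kaplan-Meier rates leave out elective procedures, whereas the exclusion covers any type. The separate table is the only named summary sure to show an elective one.

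Two stronger readings are tempting. A reader might infer that a durable TR-reduction rate is inflated, but SAP 8.3 plans no such rate, and its grade-reduction percentages are at discharge. A reader might also infer that most re-interventions are for recurrent or paravalvular regurgitation and so are TR failures by nature. The documents give no such breakdown. Appendix A covers any procedure that repairs, adjusts or replaces the device or native valve, and protocol Table 4 also anticipates thrombosis, stenosis and endocarditis.

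A further fair point is that keeping re-intervened patients as failures, while deaths and withdrawals still drop out, gives a mixed denominator. The fix has to make that visible.

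**Conclusion.** The point holds for the TR-class percentages after discharge, the moderate-or-less percentages and the paired tests. They carry an As-Treated label but are conditional on no re-intervention, and the exclusion is related to the outcome. Read as success without re-intervention, the percentages are too high by p × f. That is negligible at a 1% re-intervention share and comparable to or larger than the planned 90% half-width at 5%, depending on p. All of these sizes rest on assumed rates and on reading the exclusion as covering every later visit.

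The documents do not support saying that the echo results are overstated outright. The size is unknown, the direction depends on treating re-intervention as failure, and the declared discharge endpoint is almost untouched. Severity is modest: the study is a descriptive feasibility study with no success threshold for TR grade, and re-interventions are reported elsewhere.

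**What to change.** In SAP 8.3:

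1. State that the exclusion applies to all visits after the re-intervention and that earlier echoes are kept.
2. Keep the exclusion for continuous haemodynamic measures, where a value obtained after a second procedure does not describe the original valve.
3. In the TR-grade table and the moderate-or-less percentages, add a re-intervened category covering elective and non-elective procedures. Keep it in the denominator, counted as not achieved, including at visits after an explanted patient has left the study.
4. Show beside each visit the numbers who died or exited, so that the denominator is clear.
5. Keep the planned exclusion version and the paired tests, labelled as conditional on no re-intervention.

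The cost is one extra row in existing tables, a short footnote and a slightly less favourable percentage. No new data are needed.

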## 8.4 Clinical and Functional Endpoints and Parameters

The clinical and functional endpoints and parameters will be presented in the AT population.

All-cause mortality rates, heart failure hospitalization rates, and non-elective tricuspid valve re-intervention (percutaneous or surgical) rates at 12 months and annually thereafter and the corresponding 95% confidence intervals will be computed using Kaplan-Meier estimates with the standard errors being computed using Greenwood's formula.

Volume overload assessed by serial measurements will be summarized at each timepoint using descriptive statistics.

NYHA class will be assessed at baseline, 1 month, 6 months and annually up to 5 years. The distribution (numbers of patients and percentages) in the various NYHA classes will be tabulated and plotted for each timepoint.

Change from baseline in NYHA class, body weight, ankle circumference measurement, and edema assessment will be presented as shift from baseline for each of the pre-specified follow-up periods. Paired t-test (for continuous data) or Wilcoxon signed-rank test (for categorical data) will be performed comparing the following timepoint with the screening/baseline data. Patients who are missing a baseline or follow-up value will be excluded from the paired analysis.

Quality of life (KCCQ, SF-36v2) and functionality (6MWT) measurements will be summarized at each visit using descriptive statistics. Change from baseline at corresponding follow-up visits will be summarized by mean and standard deviation. Patients who are missing a baseline or follow up values will be excluded from the analysis. For the analyses of 6MWT, patients unable to perform the walk due to a medical reason will be considered to have walked an actual distance of zero.

Patient Preference Survey at baseline will be performed and reported by Edwards Global Health Economics and Reimbursement (GHER) separately.

Revision Date: Au		ugust 1, 2022	Rev	For Use Only by Affiliates of Edwards Lifesciences	Page 16 of 18
Edwards	Title	Statistical Analysis P	lan foi	CEND Study	(2019-06)

The number and percentage of patients who had clinically significant abnormal laboratory parameters (out of normal range) collected per protocol will be summarized at each visit.

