8.6. Study Exit Criteria and Procedures

All patients that sign an informed consent document for this study will have the study exit reason documented in the medical record and on the appropriate eCRF. Patients may exit the study for any of the following reasons:

- **Screen Failure:** Patients who are consented to participate in the study, but do not fulfill enrollment criteria.

- **Study Device Attempted but Not Implanted:** Enrolled patient for whom the implant procedure was prematurely aborted will be followed either for 30 days (for only safety evaluations) OR until resolution, stabilization, or is adequate explanation of any implant-related AEs and then exited from the study. Examples include:
 - Procedure attempted (i.e. skin incision to introduce the EVOQUE System) but patient did not receive a study device
- **Study Device Re-intervention/Explant:** Patient who has a surgical re-intervention for study device explant will be followed for 30 days after the re-intervention for safety evaluations only or until resolution of any AEs related to the re-intervention and then exited from the study. Note: a patient who has a percutaneous re-intervention where the study device remains in place will continue to be followed for the duration of the study.
- **Withdrawal**
 - **Patient Withdrawal:** A patient may voluntarily withdraw from the clinical study at any time, without penalty or loss of benefits to which they are otherwise entitled.
 - **Physician Withdrawal:** An Investigator also has the right to withdraw a patient if s/he feels it is in the best interest of the patient to do so.
- **Patient death**
- **Lost to Follow-up**
 - If a patient cannot be reached for a follow-up visit, the Investigator will document contact efforts and/or efforts to obtain hospital records in the appropriate eCRF. If a patient cannot be reached in any way, or misses a visit, the patient will be considered “unable to contact” for that time interval.
 - After 3 documented unsuccessful attempts to make contact, a certified letter will be sent to the patient’s residence. If there is no response after a certified letter is sent, the patient will be classified as “lost to follow-up”.
- **Completion Per Protocol**

Withdrawn patients will not have any study follow-up visits or procedures after the time of study exit. All data collected up until the time of withdrawal, including imaging studies such as echocardiography scans, will be analyzed.

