11.9. Investigational Device Explants

An Edwards' study device that is explanted at any time during the study should be returned to the Sponsor for evaluation.

Once the study device is explanted, the patient is followed for 30 days after the explant, unless there is an ongoing related adverse event and its outcome is not deemed resolved by the Investigator. Return kits for explanted devices will be provided upon request by the clinical monitor or study team.

12. Statistical Analysis

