#### DEFINITIONS 5.

#### 5.1 Analysis Dates and Days

Reference Start Date and Day 0

The reference start date is defined to be the date of the index procedure. The index procedure is defined as the time the first skin incision for the study device is established. If a patient has multiple procedure forms, information will be presented on the procedure with the first date when the site has indicated that the interventional skin incision for study device is performed. If no form has this indicated, then the procedure information corresponding to the date of the first procedure will be used.

The reference start date is considered to be day 0.

Last Participation Date

The Last Participation Date is defined as the last date the patient was seen (refer to the programming convention for complete details).

Last Participation Day

Last Participation Day = Last Participation Date – Reference Start Date

Note: Last Participation Day is used as censor day for Kaplan-Meier analysis.

	Revision Date: August 1, 2022		Rev		For Use Only by Affiliates of Edwards Lifesciences	Page 12 of 18
Edwards	Title	Statistical Analysis P	lan foi	 TRIS	CEND Study	r (2019-06)

• Study Day

Study Day = Date – Reference Start Date

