### 8.1 Safety Endpoint

The safety endpoint of MAEs at 30 days shall be analyzed via the Kaplan-Meier method for the Enrolled and AT populations. In addition, the event rates of individual component of MAEs will also be calculated at 30 days, 6 months, and annually until 5 years post-procedure by the Kaplan-Meier method:

- Cardiovascular mortality •
- Myocardial infarction (MI) •
- Stroke •
- Renal complications requiring unplanned dialysis or renal replacement therapy •
- Severe bleeding (includes fatal, life-threatening, extensive, or major bleeding, as defined by MVARC) •
- Non-elective tricuspid valve re-intervention, percutaneous or surgical •
- Major access site and vascular complications •
- Major cardiac structural complications •
- Device-related pulmonary embolism

The number and percentage of patients with at least one MAE at 30 days will be summarized. The number of MAE at 30 days, 6 months, and annually will be reported as well. Additional analyses of safety endpoints using the PP population will be performed if there is/are a clinically meaningful difference(s) from the enrolled and AT populations.

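### The 5-year Kaplan-Meier rates for heart failure hospitalization, re-intervention and MAE components appear to censor event-free deaths, and would then overstate the share of patients with the event

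*SAP*

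**What the plan says.** SAP 8.4 uses Kaplan-Meier with Greenwood standard errors for all-cause mortality and for "heart failure hospitalization rates, and non-elective tricuspid valve re-intervention (percutaneous or surgical) rates at 12 months and annually thereafter". SAP 8.1 says that "the event rates of individual component of MAEs will also be calculated at 30 days, 6 months, and annually until 5 years", again by Kaplan-Meier. The components include cardiovascular mortality and non-elective re-intervention. Protocol 12.3 and 12.4 also name Kaplan-Meier.

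The censoring rules are spread over four places:

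- SAP 6.1: "Patients without events will be censored at their last participation date in the study". Event-free patients who remain in the study are censored at the database extract date instead.
- SAP 5.1: "Last Participation Day is used as censor day for Kaplan-Meier analysis". The last participation date is the last date the patient was seen. Full details are left to a programming convention that is not part of the documents.
- SAP 6.2: for time-dependent endpoints, withdrawal and loss to follow-up lead to censoring. Death is not mentioned.
- Protocol 8.6: "Patients may exit the study for any of the following reasons". Patient death is one of the listed reasons.

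Neither document mentions competing risks or cumulative incidence.

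**The concern.** A patient who dies without a heart failure hospitalization cannot be hospitalized later. Kaplan-Meier with that patient censored assumes that the remaining risk is the same as that of the patients still alive. The result is the risk in a hypothetical cohort in which nobody dies first, and it is larger than the proportion of treated patients who are ever hospitalized. The excess grows with follow-up and mortality. Follow-up here is 5 years, and Protocol 7.1 expects a mean age of about 78.

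SAP 2.1 makes guidance for future study designs an objective. A designer who took the 5-year figure as an event proportion, without modelling death separately, would expect too many events. A reader of the long-term safety tables would overstate how many patients had each event.

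**Working it through.** **Does the plan censor event-free deaths?** Death is a study exit (Protocol 8.6), so such a patient does not remain in the study and the database-extract rule does not fit. The rule that remains is censoring at last participation (SAP 6.1, SAP 5.1). This is the natural reading, but no sentence states it.

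**Inputs.** The documents state no mortality, hospitalization or component rate, so there is no figure of the plan to reproduce. The assumptions are:

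- 5-year all-cause mortality M: 20%, 33%, 45% or 55%.
- First-hospitalization hazard h: 0.10, 0.15 or 0.25 per year.
- Death hazard d before hospitalization and k·d after it, with k = 1, 2 or 3. For each case d is solved so that 5-year mortality equals M.

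**Formulas at time t, constant hazards.**

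- One minus Kaplan-Meier, deaths censored: 1 − exp(−h·t)
- True share with the event: h/(h+d) × [1 − exp(−(h+d)·t)]
- Survival, used to solve d: exp(−(h+d)t) + h/(h+d−k·d) × [exp(−k·d·t) − exp(−(h+d)t)]

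**Largest case.** h = 0.25, M = 55%, k = 1, so d = −ln(0.45)/5 = 0.160. Kaplan-Meier gives 1 − exp(−1.25) = 71.3%. The true share is 0.25/0.41 × [1 − exp(−2.05)] = 53.2%. The gap is 18.2 points before rounding. With k = 2 or 3 the true share is 57.5% or 59.9%, and the gap falls to 13.9 or 11.4.

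**Smallest case in this grid.** h = 0.10, M = 20%, k = 3, d = 0.032: 39.3% against 36.6%, a gap of 2.7 points.

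**Early-peaking hospitalization.** The hazard is h in year 1 and h/3 in years 2 to 5. For h = 0.10 the cumulative hazard is 0.10 + 4 × 0.033 = 0.233, so Kaplan-Meier gives 20.8%. With M = 20% and k = 3 the true share is 19.5%, a gap of 1.3 points.

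Overstatement of 5-year heart failure hospitalization, in percentage points:

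| Assumed pattern | M = 20% | M = 33% to 55% |
|---|---|---|
| Constant hazard, k = 1 to 3 | 2.7 to 5.9 | 4.8 to 18.2 |
| Early-peaking, k = 1 | 1.6 to 3.1 | 2.7 to 9.5 |
| Early-peaking, k = 3 | 1.3 to 2.1 | 2.3 to 7.0 |

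A rarer event also gives less. At a constant 0.05 per year (22% at 5 years) and M = 20%, the gap is 1.8 to 2.2 points. Over the constant-hazard grid the maximum is 5.2 points at 2 years and 1.6 at 1 year.

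**Cardiovascular death.** Non-cardiovascular death competes. With constant hazards and cardiovascular share s of deaths, Kaplan-Meier gives 1 − (1−M)^s and the true share is s·M. At M = 20%, s = 0.8: 16.3% against 16.0%, a gap of 0.3. At M = 55%, s = 0.5: 32.9% against 27.5%, a gap of 5.4.

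**Other components.** Put h = −ln(1−R)/5 and d = −ln(1−M)/5, where R is the 5-year Kaplan-Meier risk. For R of 5% to 10% the gap is 0.5 to 3.1 points. For R of 20% to 30% it is 2.0 to 2.9 points at M = 20% and 3.4 to 8.8 at 33% to 55%. It is smaller if much of the risk falls in the first 30 days.

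**30-day MAE.** With a 22% risk and non-cardiovascular death at 0.16 per year: 22.0% against 21.86%, a gap of 0.14 points.

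**The case against.** **The premise is an inference.** SAP 6.2 names only withdrawal and loss to follow-up, and SAP 5.1 defers to a convention that a reader cannot see. That stands. The documents do not demonstrate a bias. They leave the handling of death unstated, with censoring as the natural reading. If the convention does something else, the SAP still needs to say so.

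**Kaplan-Meier is a legitimate quantity.** Under independence it estimates the net risk, and the SAP never calls it the share of patients affected. A designer who models death separately needs the event-specific hazard behind it. The excess also raises adverse rates, so it does not flatter the device. All this is right. It lowers the stakes but does not tell the reader which quantity is reported.

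**Other outputs help.** All-cause mortality is reported alongside, and SAP 9.1 tabulates primary cause of death at 30 days and annually from 1 year. This is partial mitigation: the percentages may use the SAP 6.1 denominator, which appears to leave out event-free patients not followed to the end of the visit window.

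**Stronger readings that the documents do not support.**

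- A reader might infer that the excess must be at least several points. It need not be: the low ends of the constant-hazard row are not floors, as the early-peaking rows show. The expected age supplies no event or mortality rate.
- A reader might infer that the 30-day safety endpoint is compromised. It is not, to any material degree.
- A reader might see a separate gap in surgical explant, because "Patient who has a surgical re-intervention for study device explant will be followed for 30 days after the re-intervention" and, in Protocol 11.9, "Once the study device is explanted, the patient is followed for 30 days after the explant". But explant is an exit in the same Protocol 8.6 list as death. The reading that censors deaths censors these patients too, so it cannot also be called unaddressed.

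**Conclusion.** The point holds in a limited form. If event-free deaths are censored, as the text implies, the direction is certain whenever deaths occur before events that would otherwise have followed. The size is purely illustrative. For 5-year heart failure hospitalization it is about 1 to 6 points at 20% mortality and about 2 to 18 points at 33% to 55%. The upper ends need frequent hospitalization at a constant hazard and no excess mortality afterwards. Cardiovascular death (about 0.3 to 5.4 points) and rare components are affected less. A component as common and as late as hospitalization could be affected as much.

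No test or success criterion is involved. The matter concerns descriptive rates, mainly beyond 2 years, and their use in planning later studies. The change is worth making because it is cheap, but the study's conclusions do not hang on it.

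**What to change.** - Keep Kaplan-Meier for all-cause mortality and for the 30-day MAE endpoint.
- For heart failure hospitalization, re-intervention, cardiovascular mortality and the other MAE components beyond 30 days, report the Aalen-Johansen cumulative incidence with its own variance. Death is the competing event; for cardiovascular mortality it is non-cardiovascular death.
- Keep the Kaplan-Meier curves as a supplementary display.
- State the handling of event-free death in SAP 6.1, 8.1 and 8.4.
- List the change from Protocol 12.3 and 12.4 in SAP section 10.

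The cost is a few sentences and a standard analysis. No new data are needed, since deaths and their causes are already collected and summarized. The downside is slightly less direct comparability with Kaplan-Meier figures in other device reports, which the supplementary display covers.
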